One new molecular biology method is potentially capable of not only discerning an infectious etiology, but also providing additional information about genetic, environmental, and immunologic contributions to sarcoidosis. This technique involves the differential display of reverse transcription (RT) PCR products, and is termed differential display PCR (DD-PCR). DD-PCR involves the use of arbitrary oligonucleotide primers to amplify most mRNAs found in the cell using reverse transcription PCR, with modifications to target cDNA coding regions (Amac et al, 1994; Brenner et al, 1994; Gullans et al, 1994; Kojima et al, 1994; Liang and Pardee, 1992; Liang et al, 1992; Randall et al, 1994). For the ACCESS study, the DD-PCR reaction will be performed using RNA from cases and controls, and the PCR products from each reaction will be compared on polyacrylamide sequencing gels.

The priority with DD-PCR is to detect bands that are consistently observed in one group (either the case or control), but are infrequent in the other group of paired samples. Using recent modifications, including the normalization of background noise, the unique bands that are present in cases but not controls will be presumed to represent candidate genes specific for sarcoidosis. Such candidate genes could be of host origin or could represent genetic materials from an infectious agent that is causally related to development of sarcoidosis. To identify and characterize the genes, unique bands are eluted from the gel, reamplified, and cloned into plasmids. The clones are sequenced and subjected to computer analysis to identify the genes and determine whether, for example, there is a specific gene of viral or bacterial origin.

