3.6.2 Molecular Analysis of Sarcoidosis-Specific Genes

Building upon the hypothesis that sarcoidosis represents "the response to an exogenous agent in a genetically susceptible individual," this project will use a state-of-the-art molecular biologic technique, the differential display polymerase chain reaction, to identify genes that are expressed in cases with sarcoidosis but not in matched controls. This method provides the opportunity to screen for a wide variety of exogenous agents, such as viral, fungal, and mycobacterial agents as well as previously unidentified organisms. In addition, there is the opportunity to detect candidate endogenous genetic material that is being expressed in cases but not controls, potentially leading to identification of candidate genes which could provide the basis for future genetic studies using molecular epidemiologic approaches.

Initial screening will be performed on 20 cases and 20 controls from one Clinical Center (Beth Israel Deaconess Medical Center) to generate 50 candidate gene markers for sarcoidosis. In order to broaden the opportunity to identify either exogenous or endogenous genetic materials that are preferentially expressed at different times during the natural history of sarcoidosis, there will be no restrictions on the category or stage (Scadding, 1961) of sarcoidosis among cases whose specimens are analyzed. If promising candidate genes are found, an attempt will be made to substantiate the initial findings by performing Northern blot analysis on a different group of 10 cases and 10 controls, using the prioritized gene products. If there are not any promising candidate genes, the initial screening will be extended to include an additional 10 cases and 10 controls.

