3.6.5 Defining an Etiologic Sarcoid Antigen in the Kveim Reagent

The Kveim-Siltzbach reaction is a localized, delayed granulomatous response to the intradermal injection of sarcoid tissue in patients with sarcoidosis. World-wide, the reaction occurs in 70-80% of individuals with early sarcoidosis and rarely in normal individuals or in other granulomatous disorders. The protracted time course and granulomatous features are strikingly similar to the Mitsuda reaction to lepromins in tuberculous leprosy suggesting that the reaction is due to an unidentified "sarcoid" antigen. Recent studies of T-cell receptor gene expression at sites of Kveim-Siltzbach reactions support the concept that the Kveim reaction is T cell antigen-driven. The goal of this special laboratory study is to establish methods for defining the antigenic component contained in Kveim-Siltzbach reagent that is responsible for its in vivo reactivity in sarcoidosis to test the hypothesis that Kveim-Siltzbach reagent stimulates specific lung and blood T-cell subsets from patients with sarcoidosis. Three specific aims are proposed: determine if bronchoalveolar lavage (BAL) cells from cases are stimulated by validated Kveim reagent; determine if Kveim reagent preferentially stimulates blood mononuclear cells of cases compared with controls; and determine if Kveim-active T-cell lines can be established from the lung or blood of cases and assess the T-cell phenotype of these T-cell lines.

To accomplish these aims, lung and blood T cells are isolated and cultured with validated Kveim reagent and co-stimulating factors such as IL-2 and IL-12. Antigen reactivity is measured by proliferation (³H-thymidine uptake) and cytokine production after various time periods. Long-term T-cell lines with reactivity to Kveim reagent are established for repeated testing of components of Kveim reagent. These T-cell lines are analyzed with respect to T-cell receptors that will also be analyzed in situ in histologic preparations of sarcoid tissue. The development of an in vitro Kveim assay would allow a biochemical analysis of active "sarcoid" antigenic component in Kveim-Siltzbach reagent and potentially define the etiologic agent of sarcoidosis. A power analysis has

preferentially simulates blood mononuclear cells of cases compared with controls. All cases and controls will be selected from those enrolled at the Johns Hopkins University School of Medicine.

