Multiorgan disease is defined as tissue confirmation in at least one organ, and either clinical or pathological involvement in another organ(s), as outlined in Table 6-1. The record of organ involvement for cases is based on abnormalities ever observed in the set of definitions in use November 1996 - March 1998, and in the revised definitions in use starting April 1998. The revisions made to the criteria for organ involvement in April 1998 were clarifications of wording, deletion of evidence of treatment response as a criterion (because almost none of the ACCESS cases have had a definitive course of treatment at the time of study entry and some of these abnormalities may respond to the same treatment if used for other diseases), and regrouping of the categories into those that are common, those that are unusual but serious, and other organ involvement.

Individuals with chronic beryllium disease are excluded from the study. Potential cases with occupational histories indicating possible beryllium exposure are excluded from the study unless both blood and bronchoalveolar lavage proliferation studies indicate a negative response to beryllium. Fungal lung disease and tuberculosis should be ruled out. Specifically, all cases should have acidfast bacillus (AFB) and fungal cultures of all available tissue performed and appropriately stained unless the diagnosis was confirmed by the Kveim agent. In potential cases undergoing bronchoscopy, bronchial washings should always be obtained specifically for fungal and AFB cultures. Potential cases who live in areas where histoplasmosis is endemic or who have risk factors for tuberculosis should have appropriate tests performed on tissue specimens (cultures of biopsy specimens required) to exclude tuberculosis and fungal infections (especially histoplasmosis). In particular, adequate samples should be cultured, if possible. At a minimum, slides of tissue should be stained for mycobacteria and fungi. Fungal serology and measures of H. capsulatum antigen are not expected to contribute to the diagnosis and are not used in ascertaining case eligibility. All slides for cases enrolled after September 1997 are reviewed under polarized light to determine whether birefringent material is present. A review for birefringent material on the slides of cases enrolled prior to September 1997 is performed if the slides are available.

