At least four transbronchial biopsy specimens are recommended for patients whose tissue diagnosis is approached with bronchoscopy and transbronchial biopsy. In patients who have an

6-2

atypical presentation for sarcoidosis, such as asymmetrical hilar adenopathy or asymmetrical pulmonary infiltrates, a sufficient amount of tissue must be sampled. For patients undergoing mediastinoscopy, it should be determined prior to the procedure which lymph nodes are considered abnormal so that biopsies of those nodes can be obtained rather than normal sized lymph nodes. Biopsy should be obtained of a grossly enlarged lymph node (≥ 2 cm) and not of normal sized lymph nodes.

Only newly diagnosed cases are enrolled in the study. Newly diagnosed cases are of interest for accuracy and consistency of recall. A newly diagnosed case is defined as a patient who has had tissue confirmation less than six months prior to entry into the study. Cases may have received systemic treatment for sarcoidosis during this period. The day of the biopsy that confirms the presence of sarcoidosis is defined as the day of diagnosis. Duration of symptoms or findings are noted, and this information is used in comparison of cases and controls.

All cases have a baseline evaluation including an administered questionnaire, medical history and physical examination, postero-anterior (PA) chest X-ray; tissue documentation of disease; biochemistry panel which includes total protein, albumin, alkaline phosphatase, aspartate aminotransferase (AST), alanine aminotransferase (ALT), total bilirubin, serum urea nitrogen, calcium and creatinine; complete blood count with a differential; and spirometry (with bronchodilators if clinically indicated). Additional desirable, but not mandatory, studies include angiotensin converting enzyme assay (an inexpensive measure of disease activity, but not implicated in etiologic hypotheses); slit-lamp examination conducted by an ophthalmologist; purified protein derivative (PPD) skin test; lung volumes and single breath diffusing capacity. If patients were diagnosed elsewhere, pre-treatment biochemistry and complete blood count data from specimens at the time of diagnosis may be recorded as the baseline tests.

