9.3 STUDY POPULATION

Case accrual and distribution of cases is in accordance with the procedures for examining sarcoidosis etiology as described in Chapter 6.

All patients with sarcoidosis enrolled in ACCESS within the interval described in Section 9.2 are eligible for the Clinical Course Study. Patients are not excluded from consideration if they are receiving corticosteroids or other immunomodulatory medications.

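### Cases in the DD-PCR and Kveim substudies may have been treated, no handling of treatment is stated, and case-only bands are presumed specific for sarcoidosis

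*Protocol*

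**What the plan says.** Protocol section 6.1 sets the entry window: "A newly diagnosed case is defined as a patient who has had tissue confirmation less than six months prior to entry into the study". It adds: "Cases may have received systemic treatment for sarcoidosis during this period". Section 9.3, on eligibility for the Clinical Course Study, says: "Patients are not excluded from consideration if they are receiving corticosteroids or other immunomodulatory medications". That study takes the first cases of the same series.

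Section 2.3 describes DD-PCR as a comparison of RNA from cases and controls. Section 10.2.2 shows that the RNA comes from blood mononuclear cells. The inference rule in section 2.3 is: "the unique bands that are present in cases but not controls will be presumed to represent candidate genes specific for sarcoidosis". The same section gives the aim: "The priority with DD-PCR is to detect bands that are consistently observed in one group", with the band infrequent in the other group.

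Section 3.6.2 takes 20 cases and 20 controls from one center for screening, and among those cases "there will be no restrictions on the category or stage". Promising genes go to Northern blot in 10 other cases and 10 other controls. Section 3.6.5 proposes to "determine if Kveim reagent preferentially stimulates blood mononuclear cells of cases compared with controls", measured by proliferation and cytokine production.

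Neither substudy section mentions treatment as a selection criterion, stratifier, covariate or timing rule for the draw. Section 12.3.3 gives the substudies the matched analysis of section 12.3.2, which does not name treatment either.

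**The concern.** Both substudies measure what cells are doing when blood is taken. Matching on age, gender and race cannot balance sarcoidosis treatment, because controls have no sarcoidosis to treat and section 6.4 excludes those with a history of it. A host transcript switched on by treatment could therefore appear in cases and not in controls, and the rule in section 2.3 would call it a sarcoidosis candidate.

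The later steps do not test for this. Sequencing shows whether a band is of host or microbial origin. It does not show whether a host gene was induced by disease or by drug. The confirmation set is drawn with no treatment criterion, so it carries the same imbalance.

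The protocol recognises the issue elsewhere. Section 6.1 lets pre-treatment biochemistry and blood counts stand as baseline for patients diagnosed elsewhere, but makes no parallel provision for research blood. Section 2.4 reports a fall in the lavage CD4/CD8 ratio in corticosteroid-treated patients who responded.

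In DD-PCR the possible cost is effort spent on a false candidate. In the Kveim study it is a true case response that is missed.

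**Working it through.** The protocol gives no figure to reproduce: it states neither the treated share nor a numeric rule for nominating a band. What follows is a sensitivity check.

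**From the protocol:** 20 cases and 20 controls at screening, 10 and 10 at confirmation (section 3.6.2); matched analysis by McNemar's test (sections 12.3.2.2 and 12.3.3).

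**Assumed:** a share f of cases is treated at the draw; the band appears in every treated case, in no untreated case and in no control; cases are independent; a band is nominated when the case-control split is significant at 0.05, two-sided.

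**Step 1, threshold.** For r discordant pairs all in one direction, the exact McNemar p-value is 2 × 0.5^r. For r = 5 this is 0.0625 and for r = 6 it is 0.031, so 6 versus 0 is the smallest significant split.

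**Step 2, screening.** P(X ≥ 6) with X ~ Binomial(20, f).

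**Step 3, confirmation.** P(Y ≥ 6) with Y ~ Binomial(10, f). The sets are disjoint, so the two probabilities multiply.

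| f | ≥6 of 20 | ≥6 of 10 | both stages | ≥10 of 20 |
|---|---|---|---|---|
| 10% | 0.0113 | 0.0001 | 0.0000 | 0.0000 |
| 20% | 0.1958 | 0.0064 | 0.0012 | 0.0026 |
| 30% | 0.5836 | 0.0473 | 0.0276 | 0.0480 |
| 50% | 0.9793 | 0.3770 | 0.3692 | 0.5881 |

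The last column uses a stricter reading of consistency, namely a band in at least half of the screening cases. The artefact then has about a 5% chance at f = 30% and 59% at f = 50%.

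**Step 4, can the artefact be seen within cases?** At f = 25%, 5 of 20 screening cases are treated. A purely treatment-induced band splits 5/5 treated against 0/15 untreated, and Fisher's exact p is 1/15,504, about 0.00006. At f = 50% in the confirmation set the split is 5/5 against 0/5, with p = 2/252 = 0.008. A table by treatment status therefore exposes the artefact whenever some cases are untreated.

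**Step 5, Kveim.** If treated cases responded no more than controls, the mean case-control difference would be (1 − f) times that in untreated cases: 0.70 of it at f = 30% and 0.50 at f = 50%. The direction is toward no difference.

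**The case against.** The strongest reply is that few cases may be treated and that little rides on one band. Section 6.1 says that "almost none of the ACCESS cases have had a definitive course of treatment at the time of study entry", section 2.3 looks for consistent bands, and the bands are only candidates that are sequenced and re-tested. Section 3.7 calls the study hypothesis-generating and links laboratory data with the main data. Detailed methods are in Procedures Manual Volume IV, which is not at hand, and the text of section 3.6.5 breaks off in the available copy.

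Much of this stands. At 10% treated the risk is negligible, and the finding is that the protocol is silent, not that no safeguard exists. But an unfinished course is not the same as no treatment. The linkage prescribes no treatment comparison, and consistency has no numeric threshold.

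Stronger readings are tempting but not supported:

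- A reader might infer that treatment is perfectly confounded with case status and cannot be adjusted for. That would need every case to be treated; step 4 shows the artefact separating within cases.
- A reader might test 5/20 against 0/20, or 5/10 against 0/10, by Fisher's exact test and find p = 0.047 and p = 0.033. The planned analysis is matched, and 5 versus 0 gives 0.0625.
- A reader might infer that controls take no corticosteroids. No section says so. They only have no sarcoidosis to treat.
- A reader might conclude that treated cases must be excluded. Section 9.7 ties steroid therapy to symptoms and abnormalities, so exclusion would shift the sample toward milder disease and cut against the broad sampling in section 3.6.2.

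**Conclusion.** The concern holds as a flaw in a stated inference rule. The protocol admits treated cases and then presumes that any case-only expression band is specific for sarcoidosis, with no stated step that separates disease from treatment. Treatment effects may be taken for etiology in DD-PCR; a reader might infer that they will be, but that depends on a treated share the document never gives.

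Under the assumptions above, the screening risk is small at 10% treated, about one in five at 20% and more likely than not at 30%. Passing both stages is unlikely at 30% (about 3%) and becomes substantial at 50% (about 37%).

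In the Kveim study the bias would run toward a false negative, provided that treatment suppresses the response. Section 2.4 shows only a change in a lavage cell ratio, so this is an assumption. The HLA, KM, TNF and IL-1 work uses germline DNA and is unaffected.

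**What to change.** 1. Record systemic treatment status at each specimen draw for these substudies.
2. In sections 2.3 and 3.6.2, replace the presumption with: *bands present in cases untreated at the draw and absent in controls are candidate genes*. Tabulate bands by treatment status in both the screening and confirmation sets. A band seen only in treated cases does not nominate a gene.
3. In section 3.6.5, report the Kveim case-control comparison separately for cases untreated and treated at the draw.

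Treated cases stay in, so the open sampling over category and stage is kept, and no patient's care changes. If Procedures Manual Volume IV already contains such a rule, a cross-reference would serve.

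The cost is a little more tabulation and fewer effective cases for nomination: at 30% treated, about 20 × 0.70 = 14 of the 20 screening cases, and at 50% about 10.

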6.2 CASE SELECTION

It is planned that the total study population will consist of 720 cases and 720 controls. Each Clinical Center enrolls, interviews, examines and collects blood specimens from 72 cases with sarcoidosis and enrolls, interviews and collects blood specimens from 72 matched controls during the recruitment period (November 1, 1996 through June 30, 1999).

Cases may be recruited from a variety of clinical settings, including inpatient, hospital-based outpatient, and non hospital-based outpatient. Each Principal Investigator defines, in advance, the geographic area from which the center recruits patients for the study. Permission to contact patients identified in a clinical setting must be obtained initially from the attending physician of record, in advance of study enrollment. Potential cases are informed that a payment will be given to reimburse them for parking costs, meals and other expenses (including lost time from work) at the medical center, and transportation costs.

At the time of enrollment into the study, patients are categorized according to their clinical condition at the time of initial diagnosis, i.e., the day of biopsy confirmation. Table 6-2A outlines the disease categories that were used to describe cases beginning November 1996. An additional revised classification system was used beginning September 1997 and is given in Table 6-2B. The purpose of revising the disease categories is to encourage use of information on facets of the clinical presentation of sarcoidosis that were not readily appreciated in the hierarchical, initial classification of disease categories. This information is used in ACCESS to assess the spectrum of clinical sarcoidosis presentations represented among the ACCESS cases.

Initially cases are recruited at each participating Clinical Center sequentially without regard to the proportion in each category. If cases are identified from more than one patient source (e.g., different clinics or practices) within the Clinical Center, efforts are made to enroll every patient from each patient source over the period of the study year. Clinical Coordinating Center staff review the distribution of enrolled cases periodically to ensure that appropriate proportions of cases in each category are enrolled by the end of the recruitment period. Assessment occurs after each 150 incident cases have been enrolled in the study. Based on each analysis, Clinical Centers may be required to adjust the proportion of cases recruited for each category.

Clinical Center Coordinators complete screening logs for data entry and submission to the Clinical Coordinating Center. Cases are considered potential participants if their records show they

6-4
satisfy sarcoidosis eligibility criteria. Those deemed eligible are invited to participate in the study. For those cases who are ineligible for further consideration in ACCESS no questionnaire data will be collected. Data collected on those who are ineligible or refuse to participate in the study include basic demographics (age, race, gender), type of health care coverage (private insurance, managed care, no insurance, Medicare, Medicaid), and reasons for ineligibility or refusal to participate. Completion of screening logs for cases was discontinued in October 1997.

6.3 CONTROL SELECTION

There is one population-based control group, selected for the study through random digit dialing. Controls are matched to cases on age (within five years), gender and self-designated race (black, white, other).

6.3.1 Random Digit Dialing Controls

Cases are matched in a one to one ratio to controls selected through random digit dialing. Random digit dialing facilitates the selection of a control group that approximates a probability sample in the population. Random digit dialing (RDD) is used to identify potential controls through an unbiased clustered random sample of households with telephones (Waksberg, 1978). Cluster sampling of telephone households and a stratified sample of age-, gender-, and self-identified racematched individuals are used (Hartge et al, 1984).

The groups selected to generate telephone numbers, Survey Sampling Inc. (SSI), and to perform the telephone recruitment of potential controls, Telesurveys Research Associates (Random Digit Dialing (RDD) Interview Group), work under the direction of the Clinical Coordinating Center. The RDD callers are responsible for making initial telephone contact with potential controls in the geographic areas of the Clinical Centers.

Once the RDD Interview Group recruiter has established the eligibility, availability and willingness of the potential control to participate, the potential control is informed that an interviewer from the Clinical Center will be in touch soon to set up an appointment to meet for questionnaire

administration and phlebotomy. Potential controls are informed that a payment will be given to them after they complete the study interview to reimburse them for parking costs, meals and other expenses (including lost time from work) at the medical center, and transportation costs.

RDD Interview Group sends the name, address and telephone number by facsimile transmission to the Clinical Center and the Clinical Coordinating Center. As soon as possible the potential control is called back by Clinical Center staff to confirm that the potential control is eligible and is still interested in participating in ACCESS. At the same time as efforts are being made to contact the potential case by telephone, a letter on the medical center letterhead is sent to the potential control. If the individual agrees, Clinical Center staff arrange an appointment for an interview at the Clinical Center or another mutually acceptable location. Once the interview and phlebotomy have been completed, the Clinical Center notifies the Clinical Coordinating Center that the match has been completed. If the potential control refuses to comply with the study requirements or is ineligible, the Clinical Center notifies the Clinical Coordinating Center that another potential RDD control should be identified. For potential controls who are ineligible or refuse to participate, reasons for ineligibility or refusal are recorded and, if feasible, information on type of health care coverage is collected.

